	
 1. EGFR mutated (common mutations), TKI-naïve advanced NSCLC treated with Gi(1)otrif[®] as the first-line treatment for NSCLC within the approved label will be included 2. Patients treated within clinical trials are excluded 3. Patients still on treatment with Gi(1)otrif[®] will be excluded unless treatment period is ≥ 6 months
Variables:	
Primary outcomes:
 
Safety outcomes:
 
Percentage of subjects with adverse drug reactions by severity class
 
Effectiveness outcomes:
 
Time on treatment with Gi(1)otrif[®]
 
Time to progression with Gi(1)otrif[®]

Data sources:	NIS based on existing data from medical records of patients.
Study size:	At least 200 patients. ≥ 200 patients are planned based on feasibility aspects and assumptions.
Data analysis:	
Safety data will be analysed in a descriptive manner. Incidence and severity of adverse drug reactions will be summarized and displayed. For patients who have dose modifications, frequency and severity of the most common AEs pre- and post-dose modification will be summarized and displayed.
 
For effectiveness analysis, both time on treatment and time to progression will be estimated using Kaplan-Meier method, and the median along with two-sided 95% CI will be displayed (use the Greenwood's formula for estimation of standard errors). Log-rank test will be applied to compare between patients with and without dose modifications.

Milestones:	
Start of data collection in May 2016
 
End of data collection in December 2016
 
Final report of study results expected in March 2017

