Afatinib 40 mg/day (oral) is approved for the treatment of patients with advanced EGFRm+ NSCLC. Dose adjustments are recommended based on pre-defined tolerability criteria. A post-hoc analyses of the effects of afatinib dose reduction on adverse events (AEs), pharmacokinetics (PK) and PFS in the phase III LUX-Lung 3 trial showed that dose reductions occurred in 53% (122/229) of patients; the majority (86%) within the first 6 months of treatment. In patients who dose reduced, decreases in the incidences of drug-related all grade (grade \geq 3) AEs were 99.2% (20.5%) to 46.7% (4.1%) for diarrhea, 88.5% (26.2%) to 38.5% (3.3%) for rash/acne, 77.0% (12.3%) to 27.9% (0%) for stomatitis, and 44.3% (16.4%) to 36.9% (4.9%) for nail effects. Dose reductions tended to be more common in female patients, older patients, patients of Eastern Asian ethnicity, and patients with lower body weight. Dose reduction was more likely in patients with higher plasma concentrations of afatinib. On Day 43, patients who dose reduced to 30 mg \geq 4 days previously (n=38) had geometric mean plasma afatinib concentrations of 24.4 ng/mL, vs 23.7 ng/mL in patients who remained on the 40 mg dose (n=126). Median PFS was 11.3 months in patients who dose reduced during the first 6 months of treatment, vs 11.0 months in patients who did not (HR=1.25 [95% CI, 0.91–1.72]). [ASCO 2015, Yang et al, # 8073] ([P15-05676](#)).

Post-hoc analyses from LUX-Lung 3 suggest that tolerability-guided dose adjustment of afatinib is an effective measure to reduce treatment-related AEs without affecting therapeutic efficacy:

- The frequency and severity of treatment-related AEs was lower following dose reduction
- Tolerability-guided dose modification reduced the inter-patient variability of afatinib exposure, while maintaining efficacious plasma levels
- Efficacy outcomes were similar in patients who dose reduced due to AEs versus those who did not

This real-world data (RWD) study will help to understand if dose modifications are done similar as in LUX-Lung 3 trial and if the outcome on safety and effectiveness are as in trial settings.

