9.5 STUDY SIZE

The post-hoc analysis of LUX-Lung 3 providing the rationale for this study was based on 229 patients with 53% patients experiencing dose reduction. With a sample size of 200 we would be in the same range as in the LUX-Lung 3 analysis which provided robust data. It will be sufficient to analyse the effects of dose modification on patients' safety and effectiveness and to compare it with data from LUX-Lung 3 trial descriptively.

Based on feedback from physicians we expect 25-30% patients starting with a lower dose.

There will be around 50 patients starting with a modified dose, and around half of them with further de-/escalation. This is a sufficient sample size to get some impression on the reasons of a modified starting dose in real-world setting.

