9.7 DATA ANALYSIS

9.7.1 Main analysis

All collected data will be analysed separately for patients starting with 40mg and \leq 30mg. Although due to anticipated low sample size in patients starting with \leq 30mg, it will be mainly for exploratory purpose. Baseline demographics will be analysed with descriptive statistics (N, median, mean, 25%, 75% percentile, SD) and compared descriptively between patients who have dose modifications within the first 6 months of Gi(l)otrif[®] treatment and those who do not. All the demographics, safety and efficacy data from this study in real-world setting will be compared with data from LUX-Lung 3 trial in descriptive manner.

Analysis of Safety:

[figure not shown]
Safety analysis will include all patients treated with Gi(l)otrif[®] and be descriptive in nature. Incidence and severity of ADRs according to Common Terminology Criteria for Adverse Events (CTCAE) criteria (version 4.0) ([R15-5988](#)) when available will be summarized and displayed in number/percentage. For patients who had Gi(l)otrif[®] dose modifications within the first 6 months of Gi(l)otrif[®] treatment, frequency and severity of the common ADRs pre- and post-dose modification will be analysed (\geq 40mg vs $<$ 40mg; and \geq 30mg vs $<$ 30mg). Missing or incomplete ADR dates will be imputed according to BI internal SOPs.

Analysis of Effectiveness:

Effectiveness analysis will include all patients treated with Gi(l)otrif[®]. Time on treatment is from the date of first dose of Gi(l)otrif[®] treatment to the date of last dose of Gi(l)otrif[®] treatment. Time to progression is from the date of first dose of Gi(l)otrif[®] treatment to the earliest date of documented progression (clinical, radiographic or both clinical/radiographic progression) or death. Time on treatment and time to progression will be estimated using Kaplan-Meier method, and the median along with two-sided 95% CI will be displayed (use the Greenwood's formula for estimation of standard errors). Log-rank test will be applied to compare between patients with and without dose modifications. Time on treatment and time to progression will be compared between patients who dose reduced to $<$ 40 mg within the first 6 months of Gi(l)otrif[®] treatment and those who remained on Gi(l)otrif[®] 40 mg once daily. This is in analogy to the analysis made on LUX-Lung 3 where a cut-off of 6 months was used as most dose reductions occur during this time.

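### The visible plan compares effectiveness by log-rank test with no hazard ratio or interval, and at the planned size non-significance alone cannot rule out a hazard ratio near 1.25

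*Protocol*

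**What the plan says.** The primary objective (Protocol section 8) is to assess how dose modification affects adverse drug reactions, time on treatment and time to progression. The last two are primary outcomes in section 9.3.2.1.

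For these endpoints section 9.7.1 plans Kaplan-Meier curves, and "the median along with two-sided 95% CI will be displayed". It then says: "Log-rank test will be applied to compare between patients with and without dose modifications". It adds a specific contrast: "Time on treatment and time to progression will be compared between patients who dose reduced to" below 40 mg in the first six months and those who stayed on 40 mg. That contrast is modelled on the LUX-Lung 3 post-hoc analysis. The visible part of the SAP (section 1) defines the two times and their censoring, but no between-group estimate.

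Section 7 reports the LUX-Lung 3 result as a median PFS of 11.3 months in patients reduced early, "vs 11.0 months in patients who did not (HR=1.25 [95% CI, 0.91–1.72"]), and summarises it thus: "Efficacy outcomes were similar in patients who dose reduced due to AEs versus those who did not".

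Section 9.5 gives no power or precision figure. Its argument is: "With a sample size of 200 we would be in the same range as in the LUX-Lung 3 analysis which provided robust data", followed by "It will be sufficient to analyse the effects of dose modification on patients' safety and effectiveness". The abstract adds that "≥ 200 patients are planned based on feasibility aspects and assumptions".

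**The concern.** A log-rank test returns a p-value. It does not say how large the effect of dose reduction is, or how large a loss the data leave open, and those are what the objective asks for. The intervals in section 9.7.1 belong to each group's median, not to the difference between groups.

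This matters because of the result the study follows up. Section 7 takes a hazard ratio of 1.25, with an interval reaching 1.72, as similar efficacy. If that ratio is reduced versus not reduced, the interval admits a 72% higher hazard with reduction. If it is the other way round, the reciprocal interval is 0.58 to 1.10 (1/1.72 to 1/0.91). Section 7 does not say which. A study built on the same comparison, of similar or smaller size, could produce a non-significant p-value and have it read the same way. Whether that p-value could tell no loss from a loss of the size LUX-Lung 3 may have estimated depends on its power, which the protocol does not examine.

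**Working it through.** **The quoted LUX-Lung 3 figures.** They agree with each other:
- Share reduced: 122/229 = 53.3%.
- SE(ln HR) = (ln 1.72 − ln 0.91)/3.92 = 0.162. The interval's centre is √(0.91 × 1.72) = 1.25.
- z = ln 1.25/0.162 = 1.37, so two-sided p ≈ 0.17.
- Implied events, with 45.8% of patients reduced: 1/(0.162² × 0.458 × 0.542) ≈ 153.

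The planned size of 200 has no alpha, power, effect or event count attached, so there is no calculation to reproduce.

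**Inputs for this study.**
- From section 9.5: 25 to 30% start on a lower dose. Of 200, that leaves 140 to 150 starting on 40 mg. Section 9.7.1 analyses the starting-dose groups separately.
- From section 7, assumed to carry over: 0.533 × 0.86 = 45.8% reduced within six months.
- Not in the documents, so assumed: two-sided 5% test, proportional hazards, and 60 to 100% of patients with an event. This gives 84 to 140 events (140 patients) or 90 to 150 (150 patients).

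**Formulas**, with d events:
- SE = 1/√(d × 0.458 × 0.542)
- P(non-significant) = Φ(1.96 − ln HR/SE) − Φ(−1.96 − ln HR/SE)
- Upper 95% limit at an observed HR of 1.0 = exp(1.96 × SE)

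For d = 84 and HR 1.25: SE = 0.219 and ln 1.25/SE = 1.019, so P ≈ Φ(0.941) = 0.83. For d = 150: SE = 0.164 and ln 1.25/SE = 1.362, so P ≈ Φ(0.598) − 0.0004 = 0.72.

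| Events | SE | Non-significant, HR 1.25 | Non-significant, HR 1.5 | Upper limit if observed HR = 1.0 |
|---|---|---|---|---|
| 84 | 0.219 | 83% | 54% | 1.54 |
| 90 | 0.212 | 82% | 52% | 1.51 |
| 140 | 0.170 | 74% | 33% | 1.39 |
| 150 | 0.164 | 72% | 30% | 1.38 |

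The last column is also the true HR at which significance and non-significance are about equally likely. Non-significance is therefore the more likely result up to an HR of about 1.38 to 1.54, depending on events.

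**If all 200 patients enter one comparison** (120 to 200 events), the chance of non-significance is 77% to 65% at HR 1.25 and 40% to 18% at HR 1.5. The upper limit at an observed HR of 1.0 is 1.43 to 1.32.

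**Cross-check by simulated log-rank tests** (exponential times, comparator median 11 months, uniform censoring over 6 to 24 or 6 to 36 months, 3000 runs per setting). Power at HR 1.25 was 17 to 29% for 140 to 200 patients. At HR 1.5 it was 49 to 58% for 140 to 150 patients and 64 to 69% for 200. These agree with the formula.

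**The case against.** The strongest reply is that the documents set no decision rule. The objective is to assess effects, the LUX-Lung 3 comparison is descriptive, and the checklist in Annex 2 marks formal hypotheses as not applicable and records that there is no a priori hypothesis. A reader might infer that the study will declare equivalence from a non-significant test, but no passage says so. The statement about preserved efficacy in section 7 is background on a cited analysis. This stands, and the point is therefore a risk of misreading. It does not remove the point: a descriptive study has all the more reason to report an estimate with its precision.

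A reader might also infer that the test would probably miss any loss up to a 50% higher hazard. The figures do not support that. At HR 1.5, significance is more likely than not in most settings, and clearly so if 200 or more patients are compared. Two hundred is a minimum, and the site figures in section 9.2 allow 200 to 300 (25 × 8 to 30 × 10). At 300, 210 to 225 would start on 40 mg, giving 126 to 225 events; non-significance at HR 1.5 would then be 38% to 14%. At HR 1.25 it would still be 76% to 62%.

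Nor would the result be uninformative. Large losses would usually be detected, and the group medians will carry intervals.

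Finally, part of the plan is not visible. The table of contents has a blacked-out entry after section 9.7.1, and the tables the SAP announces are not shown. A hazard ratio with interval may be specified there. The point is limited to the text that can be read.

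**Conclusion.** The concern holds in a limited form. The visible plan answers a primary question about the size of an effect with a test alone. At 140 to 150 patients on 40 mg, that test would be non-significant 72 to 83% of the time at HR 1.25, and about 30 to 54% of the time at HR 1.5 (lower with 200 or more patients). An observed HR of exactly 1.0 would leave an upper 95% limit of about 1.38 to 1.54. Non-significance alone therefore cannot separate no loss from a hazard increase of the size LUX-Lung 3 estimated, if that ratio is reduced versus not reduced.

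The figures rest on the assumed test level, event share, reduction rate and proportional hazards. They describe sampling error only. Grouping patients by dose changes after the start of treatment, and confounding, could shift the comparison and are separate matters.

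A reader might go further and conclude that 200 patients is wrong or that a similarity margin is required. The documents support neither. The size is based on feasibility and has no stated target, and no margin or basis for one is given. With a true HR of 1.0, excluding a margin of 1.25 with 80% power (one-sided 2.5%) would take about 631 to 636 events, and excluding 1.50 about 191 to 193. A mandatory bound would change the nature of this descriptive study.

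**What to change.** In section 9.7.1 and the SAP, for both time on treatment and time to progression:
- report the hazard ratio for reduced versus not reduced, with the direction stated, and its two-sided 95% confidence interval;
- base the effectiveness conclusion on that estimate and interval;
- add a sentence such as: A non-significant log-rank test will not be interpreted as absence of an effect of dose reduction. The confidence interval reflects sampling error only and does not account for bias from post-baseline grouping or confounding.

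In section 9.5, qualify the claim of sufficiency with the expected precision: an upper 95% limit of about 1.4 to 1.5 if the observed hazard ratio is 1.0, with the assumptions listed.

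A pre-specified limit for calling results similar is optional. If the sponsor wants one, its basis should be given before database lock. If the parts of the plan not visible here already specify the hazard ratio and interval, only the interpretive sentences and the section 9.5 statement are needed.

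The cost is a few sentences and one model output per endpoint, with no extra patients or data. The downside is that the effectiveness result may have to be reported as imprecise, and the size statement becomes less favourable.

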7. RATIONALE AND BACKGROUND

The first marketing approval of afatinib was granted on 12 Jul 2013 in the USA (trade name Gilotrif[®]) for the indication of first-line treatment of patients with metastatic non-small cell lung cancer (NSCLC) whose tumors have epidermal growth factor receptor (EGFR) exon 19 deletions or exon 21 (L858R) substitution mutations as detected by an FDA-approved test. It was approved in the European Union on 25 Sep 2013 (trade name Giotrif[®]) as monotherapy indicated for the treatment of EGFR TKI-naïve adult patients with locally advanced or metastatic NSCLC with activating EGFR mutation(s). [REDACTED]

The approval of Giotrif[®] was based on the results observed in the pivotal trial LUX-Lung 3 study. The LUX-Lung 3 study investigated the efficacy of chemotherapy compared with afatinib, a selective, orally bioavailable ErbB family blocker that irreversibly blocks signaling from epidermal growth factor receptor (EGFR/ErbB1), human epidermal growth factor receptor 2 (HER2/ErbB2), and ErbB4 and has wide-spectrum preclinical activity against EGFR mutations. A total of 1,269 patients were screened, and 345 were randomly assigned to treatment (afatinib or chemotherapy). Median progression-free survival (PFS) was 11.1 months for afatinib and 6.9 months for chemotherapy (hazard ratio [HR], 0.58; 95% CI, 0.43 to 0.78; P=.001). Median PFS among those with exon 19 deletions and L858R EGFR mutations (n=308) was 13.6 months for afatinib and 6.9 months for chemotherapy (HR, 0.47; 95% CI, 0.34 to 0.65; P=.001). The most common treatment related adverse events were diarrhea, rash/acne, and stomatitis for afatinib and nausea, fatigue, and decreased appetite for chemotherapy. Patients reported outcomes (PROs) favored afatinib, with better control of cough, dyspnea, and pain ([P13-07382](#)).

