9.2.1 Selection of study population

Site selection:

Sites in countries with launch dates prior to 1st Jan 2015 and known to prescribe Gi(l)otrif[®] on a regular basis will be chosen. Asian and Non-Asian countries will be included.

Inclusion criteria:

All consecutive patients will be included if all the following criteria are present:

- Age \geq 18 years

Protocol for non-interventional studies based on existing data

BI Study Number 1200.270

c09038525-01

Proprietary confidential information © 2016 Boehringer Ingelheim International GmbH or one or more of its affiliated companies

- Patients with EGFR mutation (common mutations), TKI-naïve advanced NSCLC, treated with Gi(l)otrif[®] as the first-line treatment for NSCLC within the approved label
- Signed and dated written informed consent per regulations. (Exemption of a written informed consent for retrospective observational studies in some countries per local regulations and legal requirements.)

Exclusion criteria:

Patient won't be included if any of the following criteria is present:

- Any contraindication to Gi(l)otrif[®] as specified in label.
- Patients with uncommon mutations are excluded as uncommon mutations are not within label in all participating countries (e.g. USA).
- Patients still on treatment with Gi(l)otrif[®] will be excluded unless treatment period is ≥ 6 months.
- Patients treated with Gi(l)otrif[®] within an interventional trial.

A log of all patients included into the study will be maintained in the ISF at the investigational site.

Patients treated with Gi(l)otrif[®] in interventional trials are excluded to ensure the non-interventional setting of this study. The threshold of ≥ 6 months treatment with Gi(l)otrif[®] for patients being still on treatment was chosen to avoid early censoring and enable collection of mature data on ADRs and treatment duration. However, patients who stopped Gi(l)otrif[®] < 6 months will be included to avoid bias. All patients fulfilling inclusion and exclusion criteria from a site will be entered to avoid bias. The maximum of 15 patients per site was chosen to avoid bias by high proportion of patients coming from one site.

BI reserves the right to discontinue the study overall or at a particular study site at any time for the following reasons:

1. Failure to meet expected enrolment goals overall or at a particular study site.

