## 1 Methods for calculation of derived variables

Age at registration: Year of registration [patient.birthyear] – Year of birth [registration.registered\_at]

Drug-related AE: All AE with relationship to Gi(I)otrif® [ae.gilotref\_relation\_1='yes']

Time on treatment: Date of last administration [endofobservation.date] - Date of first administration of Gi(I)otrif® [baseline.date]. For patients still on treatment, time on treatment will be censored at the date of data collection.

Time to progression (TTP): First date of progression [min(endofobservation.radio\_date, endofobservation.clinic\_date)] - Date of first administration of Gi(I)otrif® [baseline.date]. Patients not known to have a progression will be censored with the date of last contact. For patients still on treatment and without progression, time to progression will be censored at the date of data collection. For patients who stopped treatment and without progression or progression date missing, time to progression will be censored on the last contact date.

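### Time on treatment and time to progression run from first dose, but the groups are set by a dose reduction in the following 6 months, so immortal time favours the reduced group

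*Protocol*

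**What the plan says.** Section 9.7.1 of the protocol (Analysis of Effectiveness) includes all treated patients and measures both outcomes from the first dose. Section 1 of the SAP uses the same origin: "Time on treatment: Date of last administration [endofobservation.date] - Date of first administration of" the drug, and likewise for progression.

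Two sentences in 9.7.1 define the comparison. The first reads "Log-rank test will be applied to compare between patients with and without dose modifications" and gives no time window. The second reads "Time on treatment and time to progression will be compared between patients who dose reduced to" less than 40 mg in the first 6 months and patients who stayed on 40 mg once daily. The window is justified by analogy with LUX-Lung 3, where "a cut-off of 6 months was used as most dose reductions occur during this time". It is not described as a landmark.

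Section 9.2.1 keeps early stoppers on purpose: those who stopped treatment short of "6 months will be included to avoid bias".

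The rest of the readable 9.7.1 deals with censoring. Sections 9.9 and 9.12 discuss selection bias only, and item 5.3 of the ENCePP checklist (exposure by time windows) is ticked No. A subsection heading after 9.7.1 is blacked out, so its content cannot be judged.

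**The concern.** The groups are not known at time zero. To enter the reduced group a patient has to stay on treatment long enough to be reduced. Anyone who stops before that is placed in the comparator, so the reduced group is credited with a stretch in which it could not have the event. For time on treatment this is a logical certainty. For time to progression it holds unless the reduction came after progression, which the documents do not rule out.

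The effect of dose modification on these two outcomes is part of the primary objective. The bias pushes towards the claim in section 7 that tolerability-guided reduction does not affect efficacy. It can therefore create an apparent benefit or hide a harm, and a result that looks null would not be reassuring.

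**Working it through.** **Inputs from the protocol**
- Reduction in LUX-Lung 3 (section 7): 122/229 = 53.3%, which reproduces the stated 53%. With 86% of reductions in the first 6 months, 0.86 × 122/229 = 45.8% of all patients.
- Early reductions (section 7, the sentence starting "On Day 43, patients who dose reduced to 30 mg"): 38/(38 + 126) = 23.2% reduced by about day 39. This is a pharmacokinetic subset, so indicative only.
- Median: progression-free survival in common mutations "was 13.6 months for afatinib and 6.9 months for chemotherapy". It is used because section 9.2.1 says "Patients with uncommon mutations are excluded".
- Patients starting on 40 mg (section 9.5): 25-30% of 200 are expected to start lower, leaving 200 × 0.70 to 200 × 0.75 = 140 to 150.

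**Assumed, not in the documents:** the hazard shape; censoring uniform over 6 to 35 months (about 35 months from US approval on 12 July 2013 to 31 May 2016); two-sided 5% level; Weibull reduction times among a susceptible share of 59-63%, fitted to the shares above.

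**Planned first-dose comparison with no true effect** (reduced within 6 months against all others)

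| Event hazard | HR, fitted to 6-month shares | Log-rank false rejection | HR, also fitted to Day 43 | Log-rank false rejection |
|---|---|---|---|---|
| Constant | 0.722-0.729 | 31.6-32.9% | 0.759 | 24.4% |
| Weibull shape 1.3 | 0.824 | 15.1% | 0.855 | 11.1% |
| Weibull shape 1.5 | 0.868 | 10.0% | 0.887 | 8.8% |

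With constant hazard the group medians are about 15.8 and 11.6 months. The mechanism shows in the first 6 months: the comparator holds 54% of patients but takes 63-69% of the events.

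**Sensitivity**
- A second simulation used piecewise reduction hazards and first dose spread over the 34 months before data collection, and dropped ongoing patients with under 6 months of treatment. It gave HR 0.71 and 35% rejection at a 13.6-month median (n = 150), and HR 0.69 and 47% at 11.0 months.
- If staying on 40 mg means never reduced: HR 0.64-0.81.
- If all reductions fall in month 1: HR 0.93-0.98. This does not fit the Day 43 counts.
- If follow-up extends to 41 months: HR 0.74, 29% rejection.

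**Hidden harm.** A true post-reduction HR of 1.25 appears as 0.875 (constant hazard) to 1.081 (shape 1.5, Day 43). Interpolating on the log scale gives the true HR behind an observed 1.00:

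ln HR = ln 1.25 × (−ln HR₀) / (ln HR₁.₂₅ − ln HR₀)

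Here HR₀ and HR₁.₂₅ are the first-dose results when the true HR is 1.00 and 1.25.
- Constant hazard, HR₀ about 0.725: 0.2231 × 0.3216 / (−0.1335 + 0.3216) = 0.382, so HR 1.46.
- Shape 1.5, Day 43: 0.2231 × 0.1199 / (0.0779 + 0.1199) = 0.135, so HR 1.14.

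**Alternatives with no true effect.** The 6-month landmark gives HR 0.985-1.003 with 4.8-5.5% rejection. The time-dependent Cox model gives HR 0.992-1.004 with 4.5-5.5%.

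**The case against.** The best counter-arguments concern size, severity and remedy; the direction of the bias is not in dispute.

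- **No formal test.** The checklist (items 2.1.4 and 2.1.5) declares no a priori hypothesis, no alpha or power is set, and the comparison with LUX-Lung 3 is descriptive. False-rejection rates may overstate the consequence. That is fair, but a log-rank test is planned, and a biased hazard ratio or pair of medians misleads without a p-value.
- **LUX-Lung 3 showed no such benefit.** Section 7 reports 11.3 against 11.0 months and HR 1.25 (0.91-1.72). The reference group of that HR is not stated. Reducers there were more often older and of lower weight, so confounding may have offset the bias. The net result in this study is therefore unknown, but that does not remove the bias.
- **Assumptions.** The Weibull shapes have no source. Section 9.9 implies follow-up shorter than 31.6 months. The reduction rate among patients still started on 40 mg may be below LUX-Lung 3's: if 30% reduce within 6 months, HR is 0.76-0.89 with 6-18% rejection. Time on treatment has no figures of its own. These points change the size, not the direction.
- **Comparator.** By analogy with LUX-Lung 3, not reduced in 6 months is the natural reading, so the never-reduced figures carry less weight. The effectiveness text should still say so.
- **Landmark.** It drops the early stoppers that section 9.2.1 keeps. This stands, and is why it should not be the main analysis.
- **Blacked-out text.** A sensitivity analysis there cannot be excluded. The main comparison as written would still be the biased one.

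**Conclusion.** The concern holds. Followed as written, section 9.7.1 gives a comparison biased towards the reduced group on both effectiveness outcomes of the primary objective. At a 13.6-month median and LUX-Lung 3 reduction rates, a null effect would appear as HR 0.72-0.89, with 9-33% false rejection. An observed HR of 1.00 would match a true post-reduction HR of about 1.14 to 1.46. The size depends on how early reductions occur, on the hazard shape and on the reduction rate, and is small only if nearly all reductions fall in the first month. The direction of this component does not depend on those assumptions for time on treatment. For time to progression it requires that reductions precede progression. The net observed difference could go either way because of confounding. This should be corrected before analysis.

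**What to change.** Change section 9.7.1 and the SAP as follows, for patients starting on 40 mg:

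1. **Main comparison:** a Cox model with dose reduction as a time-dependent covariate. Each patient counts as not reduced until the recorded date of a first reduction within 6 months. A reduction after progression does not count for time to progression. State how later re-escalation is classified. Report the HR with 95% CI.
2. **Curves and log-rank test:** start at a 6-month landmark, among patients still on treatment (time on treatment) or still progression-free (time to progression).
3. **One grouping throughout:** define the comparator as not reduced in the first 6 months, and use it in the log-rank sentence too.
4. **First-dose analysis:** keep it for the LUX-Lung 3 comparison, labelled as subject to immortal-time bias.
5. **Section 9.9:** state that neither method removes confounding by tolerability or patient characteristics.

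**Cost.** This needs wording and a standard model; section 9.3 already collects modification dates. The landmark loses 1 − 0.5^(6/13.6) = 26% of patients under constant hazard, 1 − 0.5^((6/13.6)^1.5) = 18% with shape 1.5, and 1 − 0.5^(6/11.1) = 31% at an 11.1-month median. At n = 145 with constant hazard, the 95% CI factor for the HR is exp(1.96 × 0.216) = 1.53 for the first-dose analysis, exp(1.96 × 0.228) = 1.56 for the Cox model and exp(1.96 × 0.285) = 1.75 for the landmark. The 6-month limit in item 1 should change the Cox figure little, since 86% of LUX-Lung 3 reductions fell inside it. Power for an HR of 1.25 is only 17-19% (Cox) and 10-12% (landmark), so results should be read as estimates with intervals.
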